# **Statement of Compliance**

This study will be conducted in accordance with the Code of Federal Regulations on the Protection of Human Subjects (45 CFR Part 46), any other applicable US government research regulations, and institutional research policies and procedures. The Principal Investigator will assure that no deviation from, or changes to the protocol will take place without prior agreement from the sponsor and documented approval from the Institutional Review Board (IRB), except where necessary to eliminate an immediate hazard(s) to the trial participants. All personnel involved in the conduct of this study have completed Human Subjects Protection Training.

Study number: s20-01911 Version date: 3/8/2022

## **List of Abbreviations**

AE Adverse Event/Adverse Experience

EUC Enhanced Usual Care
GCP Good Clinical Practice

HIPAA Health Insurance Portability and Accountability Act

ICF Informed Consent Form
IRB Institutional Review Board
ISM Independent Safety Monitor

MBCT-T/V Telephone/video-delivered mindfulness-based cognitive therapy

N Number (typically refers to participants)

NIH National Institutes of Health

NYULH New York University Langone Health

PI Principal Investigator

RCT Randomized controlled trial

SAE Serious Adverse Event/Serious Adverse Experience

TEAM-M TrEAtment for Migraine and Mood

US United States

Version date: 3/8/2022

# 2 Introduction, Background Information and Scientific Rationale

# 2.1 Background Information and Relevant Literature

Migraine is a chronic condition with episodic attacks of head pain, nausea and/or vomiting, and/or sensitivity to light and sound. Migraine is the world's second leading cause of disability because of its high prevalence and negative impact on social and occupational functioning during a person's peak years of productivity.

A staggering 60% of people with migraine report some elevation of depressive symptoms, with 40% reporting an inability to feel pleasure. Depressive symptoms are associated with higher migraine disability (e.g., days missed of work and/or social activities), increased use of potentially harmful opioid therapies, and twice the total annual medical costs. Migraine and depressive symptoms have shared pathophysiological and neurobiological pathways and overlapping genetic profiles. Despite the significant emotional, social, and economic burden of this comorbidity, no existing treatment adequately addresses both migraine disability and elevated depressive symptoms. Development of scalable integrative treatments that address migraine disability and comorbid depressive symptoms has been identified as a major gap in migraine treatment.

Mindfulness-based cognitive therapy (MBCT) is an evidence-based, standardized treatment comprised of 8 weekly in-person classes and home practice. MBCT effectively addresses pain and depressive symptoms for a range of chronic pain conditions. Our preliminary data demonstrated that individual MBCT sessions reduced headache disability and depressive symptoms compared to treatment as usual in people with migraine. During exit interviews, participants noted that treatment delivery (in-person) and length (1.5-2.5 hour-sessions) were barriers to accessing care. Remote and abbreviated delivery can address these barriers.

### 2.2 Rationale

Preliminary data demonstrated that an abbreviated (1hr/week) 8-week group-based telephone-delivered MBCT protocol ("MBCT-T") is feasible and reduced depressive symptoms in people with hypertension. This MBCT-T protocol did not involve video-conferencing, which could enhance patient engagement and therapeutic benefit. However, the feasibility and acceptability of a video-conferenced-based protocol (MBCT-V) is unknown and has not been compared to MBCT-T. It is also unknown whether either abbreviated and remote-delivered versions of MBCT reduce depressive symptoms in patients with migraine.

Version date: 3/8/2022

Enhanced Usual Care (EUC). EUC participants in this trial will be followed similarly to randomized participants but will not receive active psychological intervention from the study. Participants will receive educational information for migraine management and depression risk reduction and referrals to mental health resources. This will be in the form of 8 weekly online education modules whose content is based on education control groups used in previous behavioral migraine and depression research as described above.

Alternative Procedures. MBCT has been shown to improve pain and depression outcomes. Other forms of psycho-education, therapy, and/or medications may be used in routine clinical care for adjunctive treatment. Study participants may thus be treated with these modalities outside of the study. Risks of these modalities are likely to be very similar to those of the study treatments. We have selected MBCT as the primary study intervention because it has been shown to improve pain and reduce depressive symptoms in a range of patient samples and is likely to provide benefits to study participants. Remote-delivered MBCT has not been wellstudied in patients with migraine and evidence is needed to determine its utility.

### 2.3.2 Known Potential Benefits

Participants in this study might benefit in a number of potential ways:

- All participants will receive information about strategies to improve migraine management and depressive symptoms. Individuals may additionally benefit from the social connections created by the group format.
- Beyond these direct benefits, participants may also benefit from knowing that the information gained from this study will be an important step in developing new treatment options for treating people with migraine and depression, and thus, may have a large impact on the health and quality of life of many individuals.

Taken together, these anticipated benefits outweigh the minimal risks to participants.

## Importance of the Knowledge to be Gained

Study number: s20-01911 Page 4 Version date: 3/8/2022

People with migraine have a high prevalence of depressive symptoms, yet accessible and scalable interventions are lacking. To our knowledge this is the first study to optimize two remotely delivered mindfulness-based cognitive therapy interventions (MBCT-T and MBCT-V) to reduce suffering among patients with migraine and with depressive symptoms. This research proposal is poised to establish strong cross-disciplinary collaborations with key experts in migraine and MBCT and will collect valuable data in preparation for the Phase III clinical trial of remotely-delivered MBCT.

# 3 Objectives and Purpose

### Aim 1. Conduct a 3-arm, multi-site pilot RCT of MBCT-T, MBCT-V, and EUC

We propose a pilot three-arm, multi-site randomized controlled trial (n=144) of MBCT-T, MBCT-V, and Enhanced Usual Care (EUC) in people with migraine (defined by the International Classification of Headache Disorders – 3) and depressive symptoms (defined by empirical cut-offs on the Patient Health Questionnaire – 9). Quantitative and qualitative feedback from patients and facilitators will be used to optimize both MBCT-T and MBCT-V treatment quality (e.g., patient comprehension) and delivery via iterative adaption and development of treatment manuals, facilitator training protocols, and fidelity measures [MBCT-T/V Adherence & Competence Scales (MBCT-TACS) and Session Fidelity Checklists].

## A. Demonstrate fidelity to MBCT-T and MBCT-V protocols across sites.

Hypothesis (H)1: MBCT-T and MBCT-V sessions (n = 96 sessions) will be administered faithfully [MBCT-TACS scores  $\geq$  2.5] across treatment arm (MBCT-T vs. MBCT-V) and site (n = 3).

#### B. Demonstrate feasibility and acceptability of MBCT-T, MBCT-V, and EUC.

H1: MBCT-T, MBCT-V, and EUC will be feasible (Primary Outcome: 75% Session Attendance) and acceptable (Primary Outcome: Client Satisfaction Questionnaire-8 (CSQ-8) score > 24) at each site.

#### C. Demonstrate feasibility of study procedures.

- H1: Recruitment rate (Primary Outcome) will be ≥ 40% at each site.
- H2: Retention rate (Primary Outcome) will be ≥ 75% at each site and in each arm.

### Aim 2. Use decision rules to determine design for future fully-powered Phase III trial.

Pre-specified decision rules for fidelity, feasibility, acceptability, and clinical utility will determine the arms of the future Phase III trial evaluating remotely-delivered MBCT for migraine disability and depressive symptoms.

# 4 Study Design and Endpoints

### 4.1 Description of Study Design

This proposal aims to set the stage for a future definitive large-scale Phase III trial in patients with migraine and depressive symptoms. For this study, we propose a pilot three-arm, multi-site randomized controlled trial (n=144) of MBCT-T, MBCT-V, and Enhanced Usual Care (EUC) in people with migraine (defined by the International Classification of Headache Disorders -3) and depressive symptoms (defined by empirical cut-offs on the Patient Health Questionnaire -9).

Version date: 3/8/2022

# Study Enrollment and Withdrawal

#### 5.1 Inclusion Criteria

In order to be eligible to participate in this study, an individual must meet all of the following criteria:

- Currently meets ICHD-3 criteria for migraine using the American Migraine Prevalence and Prevention Diagnostic Module
- Self-reported 4-14 headache days per month, with at least one attack meeting migraine criteria
- Score between 5-14 on the PHQ-9
- Aae ≥ 18
- Ability to read and speak English
- Capacity to consent
- Prospective diary-confirmed 4-14 headache days per month, with at least one attack meeting migraine criteria
- ≥1 year of migraine

#### 5.2 Exclusion Criteria

An individual who meets any of the following criteria will be excluded from participation in this study:

- Meeting ICHD-3 criteria for persistent headache attributed to traumatic injury to the head (posttraumatic headache) on the American Migraine Prevalence and Prevention Diagnostic Module
- Changes in preventive migraine medication or anti-depressant medication within 6 weeks of intake
- Changes in longer-term migraine prevention (onobotulinum toxin A, injectable or oral anti-calcitonin gene related peptide treatment; neuromodulatory device) within 3 months of intake
- Changes in acute migraine treatment started within 4 weeks of enrollment
- Comorbid psychiatric illness or clinical features that would interfere with participant's ability to participate in or receive benefit from the MBCT-T intervention, including but not limited to: active suicidal ideation; recent history of psychosis or mania; borderline, histrionic or narcissistic personality disorder; cognitive impairment; sensory disabilities; bipolar disorder; obsessive-compulsive disorder, drug use
- Prior history of engaging in formal mindfulness-based interventions including: MBSR, MBCT, Acceptance and Commitment therapy, Dialectical Behavior Therapy
- Current daily meditation practice
- Inability to adhere to headache diary during baseline evaluation period (recorded fewer than 25/28 days)
- Unwilling to maintain stable current acute or preventive medication dosages for study duration
- Any condition that would prevent being a suitable candidate or interfere with medical care needs
- Inability to adhere to headache diary during baseline evaluation period (recorded fewer than 25/28 days).

#### 5.3 Vulnerable Subjects

No vulnerable populations will be studied.

#### 5.4 Strategies for Recruitment and Retention

Two main recruitment methods will be used to identify potentially eligible participants:

## 5.4.2 Use of DataCore/EPIC Information for Recruitment Purposes

This study will also utilize electronic health records (EHR) to enhance recruitment. Study team will submit an online request in accordance with institutional protocols (Ex. DataCore at NYU, CLG and/or Atlas at Montefiore) at each site institutions to identify a list of patients with an ICD-10 diagnosis of headache seen in general neurology and primary care clinics affiliated with NYULH in the last 6 months.

At this point, the study team will reach out to prospective participants via an IRB-approved recruitment message communicating the reason they are being contacted. Interested participants will be invited to determine their preliminary eligibility by clicking on a REDCap-hosted link containing a study pre-screener. Potential subjects who are active in MyChart will be contacted via MyChart. Potential subjects who are not active in MyChart will be sent a [SAFE] email message containing the IRB-approved recruitment message.

If individuals request information regarding opting out of further recruitment for all research, they will be directed to [contact] or [name], or the equivalent opt-out procedures/contact at each study site.

Online pre-screening via REDCap will determine preliminary eligibility based on inclusion/exclusion criteria including the following (see Sections 5.1 and 5.2 for details):

- Demographic information
- Ability to consent
- Mindfulness experience
- Migraine symptoms
- Depression and other psychiatric symptoms
- Interest in the study

Participants will be directed to an online screening survey with a waiver of signed consent to assess eligibility; a phone call can be requested (if low literacy or low technology use). A cover letter will be included with the online screen that will serve as study introduction and include some consent information (due to low risk, it is not required to be signed). Participants will be asked if they are interested in future research. Contact information for individuals interested in future studies will be retained in a separate REDCap file that will not be linked to any data from the pre-screener. Individuals will be contacted after the REDCap pre-screening questionnaire to inform them of their eligibility status. Those who are preliminarily eligible will continue on to the screening phone call for further eligibility evaluation for inclusion into the study.

Version date: 3/8/2022

# 5.5 Duration of Subject Participation

Each subject will be involved in the study for 10-11 months, including up to 2 weeks of consent and screening procedures, a 1-month run-in period, baseline/M0 assessments, the 8-week intervention, and assessments at mid-intervention/M1, post-intervention/M2, and follow-ups M3, M6, and M9.

# 5.6 Total Number of Subjects and Sites

N = 144 people with migraine and mild-moderate depressive symptoms will be recruited from: NYULH (n = 48), Montefiore Health System (n = 48) and Atrium Health Wake Forest Baptist (n = 48). The n=144 will allow each site to have 2 groups within each treatment arm; for example, at the NYULH site, the total n = 48: MBCT-T (2 groups, n = 16), MBCT-V (2 groups, n = 16) and EUC (2 groups, n = 16).

#### Subject Withdrawal or Termination 5.7

#### 5.7.1 **Reasons for Withdrawal or Termination**

Subjects are free to withdraw from participation in the study at any time upon request. An investigator may terminate participation in the study if:

- Any clinical adverse event (AE) or other medical condition or situation occurs such that continued participation in the study would not be in the best interest of the participant
- The participant meets an exclusion criterion (either newly developed or not previously recognized) that precludes further study participation

## 5.7.2 Premature Termination or Suspension of Study

This study may be temporarily suspended or prematurely terminated if there is sufficient reasonable cause. Written notification, documenting the reason for study suspension or termination, will be provided by the suspending or terminating party to the investigator, funding agency, and regulatory authorities. If the study is prematurely terminated or suspended, the PI will promptly inform the IRB and will provide the reason(s) for the termination or suspension.

Circumstances that may warrant termination or suspension include, but are not limited to:

- Determination of unexpected, significant, or unacceptable risk to participants
- Demonstration of efficacy that would warrant stopping
- Insufficient compliance to protocol requirements
- Data that are not sufficiently complete and/or evaluable
- Determination of futility
- Any condition that would prevent being a suitable candidate or interfere with medical care needs

Study may resume once concerns about safety, protocol compliance, data quality are addressed and satisfy the sponsor and/or IRB.

#### 6 Psychological Intervention

#### 6.1 Intervention Description

Mindfulness-based cognitive therapy (MBCT) is an evidence-based, standardized treatment comprised of 8 weekly classes and home practice. MBCT effectively addresses pain and depressive symptoms for a range of chronic pain conditions.

Version date: 3/8/2022

#### **6.1.1** Administration of Intervention

To maintain clinical equipoise, an independent MBCT instructor will administer the remote-delivered MBCT-T and MBCT-V sessions. We will contract clinical psychologists (master's level or above) to teach MBCT who will be supervised by a certified MBCT instructor. Both MBCT-T and MBCT-V will be remote-delivered using NYULH WebEx conferencing, which allows for a 'call-in' option that does not require internet.

### 6.1.2 Make-Up Session Protocol

Participants who are unable to attend a session will be able to listen to the audio of the study session via a secure recording. The participant will schedule a time for the make-up and will receive a personalized REDCap link and will be required to input their study ID before proceeding to the next page. If they fail to input the correct study ID, the REDCap survey will end. The next screen of the REDCap survey will contain an embedded audio recording of the study session. The recording will only be available for a short window and the REDCap survey link will expire 2 hours after the participants have scheduled to listen to the make-up session. During the calls, participants are told to not state more than their first names and if a participant does add any additional information, the audio file will be edited to remove that information. The audio will be hosted through a private Soundcloud file that cannot be downloaded and is not publicly visible, and sessions will be deleted from the platform as soon as the make-up is completed.

## 6.1.3 Procedures for Training Interventionalists and Monitoring Intervention Fidelity

In accordance with recommendations in the field, the clinician will be required to have a minimum of master's level training in clinical psychology and a regular mindfulness practice of at least two years. The clinician will be licensed or will be practicing under a licensed clinician. Fidelity will be ensured by using treatment manuals, session fidelity checklists, and weekly supervision of session audio recordings to minimize drift. Treatment fidelity will be evaluated by two or more independent raters, with a minimum of 85% inter-rater reliability, using the MBCT-TACS scale.

# 6.1.4 Assessment of Subject Compliance with Study Intervention

Treatment Session Adherence is a measure of treatment feasibility. This measure will be assessed through electronic monitoring of the attendance logs of each treatment session. The number of MBCT-T/V treatment sessions attended will be recorded. A treatment arm will be considered feasible if participants attended/read 75% of sessions on average.

Homework assignment adherence is another measure of treatment feasibility. During the intervention period, participants in the MBCT groups will be asked to record the amount of assigned home-based practice they completed each week via REDCap Mobile or Gene Doe app.

The Gene Doe app, in addition to REDCap Mobile, will be used to administer the daily headache diary as well as monitor homework adherence during the baseline run-in period through the intervention and during the posttreatment evaluation period. Gene Doe is a mobile phone research platform that interfaces with REDCap for secure capture of patient-reported outcomes. The Gene Doe app data collection and functionality was reviewed by [name], [name], and [name] at NYU-MCIT who determined this app does not require full MCIT security review and have cleared Gene Doe for use in this study.

Version date: 3/8/2022

#### 7 Study Schedule and Procedures

#### 7.1 Study Schedule

[figure not shown]

Figure 1. Study 2 Design

# 7.1.1 Pre-screening (online)

- Expected to take between 15-25 minutes
- Obtain pre-screener consent via REDCap
- Online screening questionnaires

## 7.1.2 Further Eligibility Screening (phone)

- Expected to take between 20-40 minutes within 2 weeks of pre-screener
- Obtain e-Consent via REDCap
- Further eligibility screening (verbal)

## 7.1.3 28-Day Baseline Run-In

- Daily diary including headache symptoms
- 28-day period to ensure inclusion/exclusion criteria for:
  - Migraine diagnosis 0
  - Minimal diary adherence (25/28 days)

# 7.1.4 Intervention Assignment & Intervention Orientation

- PI confirms final eligibility
- Participant is randomized to MBCT-T, MBCT-V, or EUC
- If randomized to MBCT-T or V, participant will be scheduled for a 30-minute orientation with the facilitator of the intervention

#### 7.1.5 Baseline/M0

- Expected to be completed in 30-45 minutes within 5 days of the start of the intervention
- Surveys via REDCap (see section 7.2.1.5 and 7.2.1.6 for details)

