#### 7.1.6 Study Intervention

Will begin once 6-8 participants are assigned to intervention CONFIDENTIAL

This material is the property of the NYU School of Medicine and NYU Langone Health. Do not disclose or use except as authorized in writing by the study sponsor

Study number: s20-01911 Page 10 Version date: 3/8/2022

Administered over 8 weeks (see section 6 for details)

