# 7.2 Study Procedures and Evaluations

#### 7.2.1 Study Specific Procedures

#### 7.2.1.1 Further Eligibility Screening

Individuals who meet pre-screening eligibility and who are interested in taking part in this study will be provided with e-Consent materials (hosted on REDCap) and will be scheduled to meet with a Research Assistant via telephone or video to review e-Consent materials, answer questions, and confirm understanding of the study procedures. If still interested, the subject will electronically sign the e-Consent and a pdf copy will be provided to them.

Individuals who meet preliminary eligibility criteria and who consent to participation in this study will stay on the call for further eligibility screening (20-40 minutes). During this eligibility interview, study staff will:

Study number: s20-01911 Page 11 Version date: 3/8/2022

Conduct a structured interview and then review responses with the study neurologist at each site to

ascertain whether the subject meets ICHD-3 criteria for migraine using the American Migraine

• Administer the PHQ-9 to assess depression and suicidality

Prevalence and Prevention Diagnostic Module

Ask additional eligibility questions as outlined in the "Phone Screener" document

Drs. [name], [name], [name], [name], and [name] will provide supervision at their respective sites on depression and migraine inclusion/exclusion criteria and will be available to address any questions regarding these criteria.

Subjects who pass this eligibility assessment will be assigned to an intervention and scheduled for a 30-minute individual orientation session with the intervention facilitator.

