#### 28-Day Baseline Run-In

Participants who meet preliminary criteria and provide informed consent will complete a 28-day baseline run-in to ensure participants meet inclusion/exclusion criteria for migraine diagnosis and the threshold for minimal diary adherence (25/28 days). During the baseline run-in, participants will complete a daily diary including headache symptoms using the REDCap Mobile App or Gene Doe app. If participants do not have a personal device, one will be provided by the research team. The application will prompt a diary entry at a time selected by the participant each evening. If a patient does not submit a daily entry, they will be alerted that the diary entry is still waiting for 12 hours. Participants will not be permitted to record retrospective data to reduce recall bias. Participants who continue to meet inclusion/exclusion criteria after the 28-day baseline run-in will be randomized to receive either 8 sessions of MBCT-T, MBCT-V, or Enhanced Usual Care.

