#### 7.2.1.4 Assessments

Please see Table 3 for an overview of assessment timeline and sections 7.2.1.6 and 7.2.1.7 for details.

Subjects will be asked to complete questionnaires online via REDCap, via REDCap Mobile App, or via Gene Doe App, (or on paper if they prefer – we will mail subjects the questionnaires).

Table 3. Schedule of Assessments

	Data collection by study personnel	Assessments completed by participants
Pre-Screening		Online Pre-screener
Screening	Recruitment Rate	Phone Screener
•	Daily Diary Completeness	Headache frequency
M-1^		Demographics
		FFMQ-15
		HMSES
		CEQ
		QIDS
		PROMIS
		Off-Protocol Co-Occurring Treatment Tracking
		HDI
		MSQ
		Survey Acceptability Questionnaires-7
Daily Diary		Headache frequency
(M-1 - M3)		Average Headache Attack Pain Intensity
M0*	Survey Completeness	SUS-Data Capture
	Daily Diary Completeness	HDI
		QIDS
		PROMIS-D
		MSQ

		HMSES
		MAIA-2
		PCS HPAQ
		MIDAS
Weekly During	Treatment Session Adherence	Safety Tracking
Intervention	Fidelity Checklist Survey Completeness	Homework Assignment Adherence
M1**	Survey Completeness	QIDS
	Daily Diary Completeness	PROMIS-D
	Attrition	HDI
		MSQ MBCT-HPI
		MAIA-2
		PCS
		HPAQ
		MIDAS
		Survey Acceptability Questionnaires-7
M2***	MBCT-TACS	CSQ-8
	Survey Completeness	FFMQ-15
	Retention Rate Survey Completeness	HMSES SUS-Treatment
	Daily Diary Completeness	QIDS
	Attrition	PROMIS-D
		Off-Protocol Co-Occurring Treatment Tracking
		HDI
		MSQ
		MBCT-HPI MAIA-2
		PCS
		HPAQ
		MIDAS
		For some: M2 Qualitative Questions (Exit
1400		interview)
M3°	Survey Completeness Daily Diary Completeness	CSQ-8 MBCT-HPI
	Attrition	SUS-Data Capture
	, and an	HDI
		QIDS
		PROMIS-D
		MSQ
		MAIA-2 PCS
		HPAQ
		MIDAS
		Survey Acceptability Questionnaires-7
M6°°	Survey Completeness	CSQ-8
	Attrition	MBCT-HPI
		SUS-Data Capture HDI
		QIDS
		PROMIS-D
		MSQ
		MAIA-2
		PCS
		HPAQ MIDAS
M9°°°	Survey Completeness	CSQ-8
	Attrition	MBCT-HPI
		HDI
		QIDS
		PROMIS-D

Version date: 3/8/2022

	MSQ MAIA-2
	PCS
	HPAQ
	MIDAS
As Needed	BSS

^ M-1 = Month -1/Baseline; \* M0 = Month 0/Pre-Intervention; \*\* M1 = Month 1/Mid-Intervention; \*\*\* M2 = Month 2/Post-Intervention; ° M3 = Month 3 (1 Month Post-Intervention); ° M6 = Month 6 (4 Months Post-Intervention); °° M9 = Month 9 (7 Months Post-Intervention)

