## Clinically Important Differences (CIDs) and statistical significance

If minimum benchmarks (see above) for all arms are met, we will move forward with **both MBCT-T** and **MBCT-V** vs. **EUC** in a fully-powered Phase III clinical trial **so long as neither version of MBCT is superior to the other based on the following analyses:** 

- 1) **MBCT-T/V Treatment fidelity**: MBCT-TACS is at least ≥0.2 points higher in the superior compared to the inferior arm, and this difference is statistically significant.
- 2) **MBCT-T/V Treatment feasibility** is at least 15% higher in the superior arm compared to the inferior arm, and this difference is statistically significant.
- 3) **MBCT-T/V Treatment acceptability** is at least 5 points higher in the superior arm compared to the inferior arm, and this difference is statistically significant.
- 4) MBCT-T/V Clinical utility: 50% responder rate for the HDI (10-point change from M0-M3) and the QIDS-SR (5-point change from M0-M3). No significance testing between MBCT-T and MBCT-V will be conducted for this outcome.

If one of the above criteria is met (i.e., one treatment meets threshold for being superior to the other), we will select this treatment to move forward with further testing in a fully-powered Phase III trial.

If we observe mixed results (e.g., MBCT-T is superior on feasibility but MBCT-V is superior on clinical utility) we will utilize results from secondary outcomes to further explore differences between the MBCT-T and MBCT-V treatment arms to inform the selection of treatment arms for the Phase III trial.

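### M0 is measured after randomisation, and nothing requires it to precede disclosure of the arm or the MBCT orientation, yet it anchors the responder rule and the Phase III effect sizes

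*Combined protocol and SAP*

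**What the plan says.** **Order of events.** The run-in text says "Participants who continue to meet inclusion/exclusion criteria after the 28-day baseline run-in will be randomized", and section 7.1.4 places the step there too: "Participant is randomized to MBCT-T, MBCT-V, or EUC". The same section adds "If randomized to MBCT-T or V, participant will be scheduled for a 30-minute orientation with the facilitator of the intervention". M0 follows in section 7.1.5: "Expected to be completed in 30-45 minutes within 5 days of the start of the intervention". The start itself is open-ended (section 7.1.6): "Will begin once 6-8 participants are assigned to intervention". Table 3 labels the visit "M0 = Month 0/Pre-Intervention", which is before the intervention, not before randomisation.

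**A conflicting passage.** Section 7.2.1.1, on the phone screen, says "Subjects who pass this eligibility assessment will be assigned to an intervention and scheduled for a 30-minute individual orientation session with the intervention facilitator". That puts assignment before the run-in and limits the orientation to no arm.

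**Use of M0.** In the Aim 2 decision rules (section 9.1), clinical utility is a 50% responder rate, with HDI response defined as a "10-point change from M0-M3" and QIDS-SR response as 5 points over the same interval. Section 7.2.1.5 names the Month 0 to 3 slopes of HDI, QIDS, PROMIS-D and MSQ as the effect sizes for planning the full trial.

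**An earlier measurement.** Table 3 also lists HDI, QIDS, PROMIS and MSQ at M-1, labelled as a baseline. Section 7.2.1.5 gives the time frames of these scales from M0 onward only.

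**The concern.** A baseline taken after allocation is safe only if allocation cannot move it. HDI, QIDS, PROMIS-D and MSQ are self-reports. If participants know what they will receive, or if one set of arms has already spent half an hour with a facilitator, expectation or contact can move the M0 score differently by arm. The move is then subtracted from, or added to, every change measured from M0. It is neither treatment effect as measured nor chance, and more participants would not shrink it.

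Three results are exposed: the MBCT-versus-EUC change contrasts, the slopes carried into the Phase III sample size, and the absolute responder rate compared with 50%.

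**Working it through.** The plan states no figure for this point, so there is none to reproduce. The check is of sequence first, then of scale.

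**1. Is M0 after randomisation?** Yes. Randomisation follows the run-in (28-Day Baseline Run-In; 7.1.4). M0 is tied to the intervention start (7.1.5), and the start waits for enough assigned participants (7.1.6). The gap between allocation and M0 therefore has no fixed length.

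**2. Is M0 after disclosure and orientation?** Not stated. Section 7.1.4 lists the orientation before M0 but says only that it is scheduled. No section says when participants learn their assignment, and none requires M0 to come first.

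**3. Which results start at M0?**

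| Result | Depends on M0? |
|---|---|
| HDI and QIDS-SR responder rule | Yes |
| HDI, QIDS, PROMIS-D, MSQ slopes for Phase III | Yes |
| Fidelity, attendance, CSQ-8, recruitment, retention (Aim 1 primary) | No |
| Headache frequency and pain intensity | No; the diary starts in the run-in |

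**4. Effect on a contrast.** Let d be the improvement at M0 in the MBCT arms caused by allocation, with none in EUC. For each MBCT participant, on average, change from M0 = change from a pre-randomisation score − d. The MBCT-versus-EUC difference in change moves by d, one for one. If a straight line is fitted through four equally spaced waves (0, 1, 2, 3) and only M0 is shifted, M0 has weight (0 − 1.5)/5 = −0.3 per month. The three-month change then moves by 3 × 0.3d = 0.9d. Adding M-1 as a covariate to such a model does not remove this, because M0 is still in the outcome.

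**5. Effect on the responder rate.** Assume change is normal with SD s and that the rate from a pre-randomisation score is exactly 50%. An improvement d before M0 gives a rate of Φ(−d/s), and a worsening gives Φ(d/s). Both d and s are assumed, since the documents give neither.

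| Scale | d | s | Rate if M0 improves | Rate if M0 worsens |
|---|---|---|---|---|
| HDI | 2 | 12, 16, 20 | 43.4, 45.0, 46.0% | 56.6, 55.0, 54.0% |
| HDI | 5 | 12, 16, 20 | 33.8, 37.7, 40.1% | 66.2, 62.3, 59.9% |
| QIDS | 1 | 3, 4, 5 | 36.9, 40.1, 42.1% | 63.1, 59.9, 57.9% |

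**6. Sampling error for comparison.** With 48 per arm and a 50% rate, the 95% half-width is 1.96 × √(0.5 × 0.5/48) = 0.141, about ±14 points before clustering. The 2-point HDI and 1-point QIDS shifts lie inside it; a 5-point HDI shift at s = 12 (16 points) does not.

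**7. Carry-over to Phase III.** Sample size scales as 1/effect². If the pilot effect were read 20% too small, the size would be multiplied by 1/0.8² = 1.56; if 20% too large, by 1/1.2² = 0.69. The 20% is illustrative.

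**The case against.** Measuring just before a group programme starts is a defensible choice, because it keeps the baseline recent after a wait of unknown length. Participants are also masked to the options and hypotheses (7.2.1.2), so someone who does not know the alternatives has less reason for arm-specific disappointment. That lowers the likelihood of a shift but does not exclude it. Masking to the options is not withholding one's own assignment, and a meeting with a facilitator is informative.

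The stakes are limited, and this stands. The Aim 1 primary outcomes do not use M0. EUC goes forward on feasibility and acceptability alone, so no decision rule turns on an MBCT-versus-EUC change. Both MBCT arms are due the same orientation, so its presence does not by itself favour MBCT-T or MBCT-V.

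The M-1 alternative has its own weakness. Participants are selected on elevated PHQ-9 scores, so change from M-1 in an uncontrolled responder rate can include regression to the mean over the run-in and the wait.

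A reader might infer more than the documents support:
- *That every change outcome is affected.* The diary outcomes have a pre-randomisation run-in.
- *That the arm is disclosed and the orientation completed before M0, in the MBCT arms only.* Timing is inferred from listing order, and section 7.2.1.1 carries no arm limit.
- *That M-1 scores are excluded from analysis.* The monthly mixed models in Planned Secondary Analyses do not name their waves; the plan is silent on which wave is baseline.

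**Conclusion.** The point holds as a gap in the schedule and in the definition of baseline. M0 is certainly after randomisation. Whether it also follows disclosure and orientation is left open, and the sections on assignment disagree. Any allocation-related shift would enter the MBCT-versus-EUC changes from M0 one for one and would also move the Phase III slopes and the absolute responder rate.

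Its size and direction cannot be known from the documents. Under the assumed SDs, a 2-point HDI shift moves a 50% responder rate by about 4 to 7 points, and a 1-point QIDS shift by about 8 to 13, up or down. A reader might conclude that the MBCT arms would fail the 50% rule. That does not follow: the example places the true rate exactly on the cut-off, where any adverse shift fails, and a favourable shift is equally possible. The case for acting is that the error would be systematic and that removing the opportunity for it is cheap.

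**What to change.** 1. Reconcile sections 7.1.4, 7.2.1.1 and the 28-Day Baseline Run-In text on when assignment and orientation take place and for which arms.
2. Require the M0 survey to be completed before the assignment is disclosed and before any orientation. State in 7.1.5 that the 5-day window lies before the start.
3. If that cannot be scheduled, take the pre-randomisation M-1 HDI, QIDS, PROMIS and MSQ scores as the baseline covariate, with only the waves after the intervention starts as outcomes. Adding M-1 to a model of the M0–M3 slope is not enough. Correct the time frames in 7.2.1.5 to agree with Table 3, so that the M-1 collection is certain.
4. In that case also report the responder rate from M-1, as a sensitivity analysis only.

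**Cost.** The preferred option is procedural wording and a tighter window between group assignment, survey, orientation and start. The fallback needs no new visit for these four scales, but the baseline is older and the uncontrolled responder rate is open to regression to the mean. MAIA-2, PCS, HPAQ and MIDAS have no listed M-1 value, so only the preferred option helps them.
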